1. PROTOCOL SUMMARY

1.1. Synopsis

Protocol Title: A Phase 2, Randomized, Double-blind, Placebo-controlled, Dose-finding Study to Evaluate the Efficacy and Safety of ALXN2050 in Adult Participants with Proliferative Lupus Nephritis (LN) or Immunoglobulin A Nephropathy (IgAN)

Brief Title: Phase 2 Study of ALXN2050 in Proliferative Lupus Nephritis (LN) or

Immunoglobulin A Nephropathy (IgAN)

Regulatory Agency Identifier Number(s)

IND: 153068

EudraCT: 2021-001426-22

NCT: NCT05097989

EU CT: 2023-504825-38-00

Rationale: ALXN2050 is a potent, reversible, oral small molecule inhibitor of complement factor D (FD), which is an essential component of the complement alternative pathway (AP). The complement system is involved in the pathophysiology of proliferative LN and immunoglobulin A nephropathy (IgAN). The objectives of this study are to evaluate the efficacy and safety of oral ALXN2050 compared to placebo, demonstrate proof of concept for efficacy of FD inhibition, and establish a dose in patients with LN or IgAN.

Objectives and Endpoints

Objectives	Endpoints					
Primary (Both Cohorts)						
To evaluate the efficacy of ALXN2050 to reduce proteinuria in participants with LN or IgAN	Percentage change in proteinuria from baseline to Week 26 (based on 24-hour urine collection[s])					
Secondary (Both Cohorts)						
	Percentage change in proteinuria from baseline to Week 50 (based on 24-hour urine collection[s])					
To evaluate the efficacy of ALXN2050 to improve measures of kidney function in participants with LN or IgAN	Achieving > 30% and > 50% reduction in proteinuria at Week 26 and Week 50 compared to baseline (based on 24-hour urine collection[s] at each time point)					
	Change from baseline in eGFR at Week 26 and Week 50					
Secondary (LN Cohort Only)						
To evaluate the efficacy of ALXN2050 on	Meeting the criteria for CRR at Week 26 and Week 50 (as defined in Section 8.1.10)					
measures of kidney function in participants with LN	Meeting the criteria for PRR at Week 26 and Week 50 (as defined in Section 8.1.10)					

Objectives	Endpoints					
	Time to the first occurrence of UPCR \leq 0.5 g/g as measured by spot urine sample					
	Achieving corticosteroid taper to 7.5 mg/day at Weeks 12, 26, and 50					
	Experience of a Renal Flare (as defined in Section 8.1.6) through Week 50					
	Experience of an Extrarenal SLE Flare (as defined in Section 8.1.7) through Week 50					

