7. DISCONTINUATION OF STUDY INTERVENTION AND PARTICIPANT DISCONTINUATION/WITHDRAWAL

7.1. Discontinuation of Study Intervention

Participants must be considered for discontinuation from study intervention if any of the following occur during the study:

- Severe hypersensitivity reaction.
- Severe uncontrolled infection.
- Development of seizures (Section 10.14).
- Use of disallowed medication (as defined in Section 6.5.2) to be considered on a case-by-case basis.
- Participants in the LN cohort receiving hydroxychloroquine will be withdrawn if a QT/QTc interval > 500 msec or an increase > 60 msec from baseline occurs and is confirmed on recheck.
- Pregnancy or planned pregnancy. Any female participant who becomes pregnant
 while participating in the study will discontinue study intervention and will be
 withdrawn from the study.
- Alexion or the Investigator deems it is necessary for the participant.
- Adverse event that would, in the opinion of the Investigator, make continued treatment with study intervention an unacceptable risk.
- Participants in the LN cohort who have 2 Treatment Failures.

Data to be collected at the time of study intervention discontinuation and follow-up and for any further evaluations that need to be completed are provided in the SoA (Section 1.3).

The reason for discontinuation of study intervention will be recorded in the source documents and eCRF.

If the study intervention is definitively discontinued, every effort should be made to have the participant remain in the study and continue the study visits as per the SoA through Week 50 (Section 1.3).

Participants who discontinue study intervention and remain in the study may receive treatment consistent with local standard practice for their disease per Investigator judgment, as applicable.

 A Safety Follow-up Visit will be performed 30 days following the participant's last dose of study intervention.

If the participant does not agree to continue with the study visits after discontinuation of study intervention, the following activities should be completed:

- ED Visit should be performed as outlined in the SoA (Section 1.3).
- A Safety Follow-up Visit will be performed 30 days following the participant's last dose of study intervention

If a participant discontinues study intervention due to an AE, including SAEs, the event should be followed as described in Section 10.3.3.

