7.2. Participant Discontinuation/Withdrawal from the Study

- All efforts should be made to ensure participants are willing to comply with study participation prior to conducting the screening procedures.
- The study staff should notify Alexion and their site monitor of all study withdrawals as soon as possible. The reason for participant discontinuation must be recorded in the source documents and eCRF.
- A participant may withdraw from the study at any time at his/her own request.
 - If the participant withdraws consent for disclosure of future information, Alexion
 may retain and continue to use any data collected before such a withdrawal of
 consent, if permitted by local requirements.
 - If a participant withdraws from the study, the participant may request destruction of any samples taken and not tested, and the Investigator must document this in the site study records.
- A participant can be withdrawn at any time in the best judgment of the Investigator for safety, behavioral, compliance, or administrative reasons, such as:
 - Pregnancy or planned pregnancy
 - Lack of efficacy
 - Participant noncompliance
 - Intercurrent illness that would affect assessment of clinical status to a significant degree
 - Unacceptable toxicity (including a clinically significant laboratory value) that compromises the participant's ability to continue study specific procedures
 - Any other condition or circumstance that that would jeopardize the welfare of participants were they to continue in the study
- At the time of discontinuing from the study, if possible, an ED Visit should be conducted, as shown in the SoA (Section 1.3). Refer to the SoA for data to be collected at the time of study discontinuation and follow-up and for any further evaluations that need to be completed.

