9.4.6.2.2. Secondary Efficacy Analyses for LN Cohort Only

The percentage of participants achieving the following secondary endpoints will be summarized by treatment group by calculating the point estimate and 2-sided 95% CI, based on exact confidence limits using the Clopper-Pearson method:

- Meeting the criteria for CRR as well as individual components of CRR at Week 26 and Week 50
- Meeting the criteria for PRR at Week 26 and Week 50
- Achieving corticosteroid taper to 7.5 mg/day at Week 12, Week 26, and Week 50
- Experience of protocol-defined Renal Flare through Week 50
- Experience of protocol-defined Extrarenal SLE Flare through Week 50
- Meeting the criteria for Treatment Failure through Week 50
- Meeting the criteria for Suboptimal Response through Week 50

Time to the first occurrence of UPCR \leq 0.5 g/g will be summarized based on spot urine samples. A Kaplan-Meier cumulative distribution curve will be generated for treatment group, and a log-rank test comparing the curves for ALXN2050 180 mg bid and placebo treatment groups will be performed. The corresponding summary table will present by treatment group the cumulative distribution function (CDF) estimate, the number of participants at risk, the number of participants responding, and the number of participants censored at each postbaseline time point. The table will also present the first quartile, median, and third quartile, along with 2-sided 95%CI, of time to UPCR \leq 0.5 g/g.

Serum albumin will be summarized at baseline and each scheduled postbaseline time point by treatment group using descriptive statistics for the observed value as well as the change from baseline.

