4.3.1.4. Complete Renal Response (LN Cohort Only)

Complete renal response (CRR) will be assessed at Weeks 26 and 50. To achieve CRR, participants in the LN cohort must meet all of the following criteria:

- A decrease in mean UPCR to ≤ 0.5 g/g based on two 24-hour urine collections obtained within 2 weeks prior to the study visit (Week 26 or 50)
- eGFR > 60 mL/min/1.73 m² or no eGFR reduction ≥ 20% from the baseline value based on the mean of 2 values. The first eGFR value must be obtained within 2 weeks prior to the study visit (Week 26 or 50) and the second eGFR value will be obtained on the study visit (Week 26 or 50)
- No treatment failure (as defined in Section 4.3.1.10)

The percentage of participants meeting the criteria for CRR as well as individual components of CRR will be summarized at Weeks 26 and 50 by treatment group by calculating the point estimate and 2-sided 95% CI, based on exact confidence limits using the Clopper-Pearson method.

Study participants with treatment discontinuation will be treated as failure to meet CRR criteria and considered nonresponders.

A bar chart will also be provided displaying the proportion of participants meeting the criteria for CRR as well as individual components of CRR at Weeks 26 and 50 by treatment group.

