4.3.1.8. Renal Flare (LN Cohort Only)

Renal flare is determined in the opinion of the Investigator in addition to the criteria outlined below and will be recorded on the Renal Flare eCRF:

- For participants who achieve CRR, a renal flare is the reproducible recurrence of proteinuria $\geq 1~g/g$
- For all other participants, a renal flare is either of the following:
 - Reproducible increase of serum creatinine > 25% higher than baseline or above the upper limit of normal, plus any one of the following:
 - Reproducible proteinuria $\geq 75\%$ higher than baseline
 - Worsening active urinary sediment compared to baseline as defined by an increase of ≥ 5 red blood cells (RBC)/high power field (hpf) or new RBC casts (based on local laboratory results from at least 2 samples)
 - Kidney biopsy demonstrating LN Class III or IV activity that was conducted since the biopsy used for eligibility
 - Reproducible doubling of the UPCR from a 24-hour urine collection compared with the lowest previous value obtained after the first dose of study intervention

Reproducibility of proteinuria requires that UPCR from a morning spot urine collection be confirmed by a central laboratory UPCR based on 24-hour urine collected within 2 weeks.

Reproducibility of serum creatinine requires 2 blood tests within a 2-week period.

The percentage of participants meeting the criteria for renal flare through Week 50 will be summarized by treatment group by calculating the point estimate and 2-sided 95% CI based on exact confidence limits using the Clopper-Pearson method.

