4.3.1.10. Treatment Failure (LN Cohort Only)

Treatment Failure is defined as the receipt of additional standard of care therapy at any time up during the study for protocol-defined renal flare, severe extrarenal SLE flare, or suboptimal response as recorded on the Additional Standard of Care Therapy eCRF.

Increase in corticosteroids for extrarenal SLE flare not meeting the protocol definition of severe extrarenal SLE flare, renal flare not meeting protocol definition for renal flare, lack of response not meeting the protocol definition of suboptimal response, other medical conditions, or surgery limited to \leq 14 days duration are **not** included in treatment failure.

Participants who meet the criteria for treatment failure may continue to receive the study intervention and stay in the study. If a participant has 2 Treatment Failures, study intervention discontinuation should be considered. If a calcineurin inhibitor (CNI) is used for additional standard of care therapy, study intervention will need to be discontinued 3 days prior to CNI administration.

The percentage of participants meeting the criteria for treatment failure through Week 50 will be summarized by treatment group by calculating the point estimate and 2-sided 95% CI based on exact confidence limits using the Clopper-Pearson method.

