4.3.1.11. Suboptimal Response (LN Cohort Only)

For the LN cohort, a suboptimal response is determined in the opinion of the Investigator in addition to the following criteria after the Week 26 Visit:

• Reproducible proteinuria ≤ 25% decreased compared to baseline based on UPCR on a 24-hour urine collection performed by central laboratory

Reproducibility of proteinuria requires that UPCR from a morning spot urine collection be confirmed by a central laboratory UPCR based on 24-hour urine collected within 2 weeks.

Participants with suboptimal response will stay in the study and continue to receive study intervention. Intensification of current standard of care or introduction of new immunosuppressive therapies are allowed per the clinical discretion of the Investigator in conversation with the Medical Monitor and will be considered additional standard of care therapy. Participants with suboptimal response will be included as treatment failure.

The percentage of participants meeting the criteria for suboptimal response will be summarized through Week 50 by treatment group by calculating the point estimate and 2-sided 95% CI based on exact confidence limits using the Clopper-Pearson method.

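### The four LN flare and failure endpoints through Week 50 are crude FAS percentages with no rule for incomplete follow-up, so cumulative risk is modestly understated

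*Protocol*

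**What the plan says.** The protocol synopsis (Section 1.1) lists the endpoints as events accumulated to Week 50, for example "Experience of a Renal Flare (as defined in Section 8.1.6) through Week 50". Protocol 9.4.6.2.2 sets the method for all four endpoints in one sentence: "The percentage of participants achieving the following secondary endpoints will be summarized by treatment group", with exact 95% limits. The SAP repeats it endpoint by endpoint:

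- Renal Flare (SAP 4.3.1.8): "The percentage of participants meeting the criteria for renal flare through Week 50 will be summarized by treatment group".
- Extrarenal SLE Flare (SAP 4.3.1.9): the same wording in substance, with severe flares also shown.
- Treatment Failure (SAP 4.3.1.10): "The percentage of participants meeting the criteria for treatment failure through Week 50 will be summarized by treatment group".
- Suboptimal Response (SAP 4.3.1.11): "The percentage of participants meeting the criteria for suboptimal response will be summarized through Week 50 by treatment group".

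SAP 4.3 bases secondary analyses on the FAS, which SAP Table 2 defines by randomization and one dose, with no follow-up requirement. SAP 4.1.4 imputes nothing for missing postbaseline data unrelated to intercurrent events and leaves the handling of intercurrent events to each analysis section. Sections 4.3.1.8 to 4.3.1.11 contain no such handling, no censoring and no person-time. The four endpoints are also absent from the key secondary estimands (SAP Table 6) and from the dosing-pause sensitivity analyses (SAP 4.3.2). SAP 6.1.8 and 6.1.11 establish that there was no treatment failure by the absence of recorded additional therapy.

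**The concern.** These are adverse outcomes that accrue over 50 weeks. A yes/no event, an FAS denominator and no imputation together make a participant who leaves early without a recorded event a non-event, however short the follow-up.

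Elsewhere the SAP does deal with incomplete data. For complete renal response, "Study participants with treatment discontinuation will be treated as failure to meet CRR criteria and considered nonresponders". For time to spot UPCR of 0.5 g/g or less (SAP 4.3.1.6), Kaplan-Meier with censoring is planned. SAP 4.1.4 also assumes that outcome data missing because of the dosing pause or COVID-19 are missing at random, and scoring those participants as event-free does not match that assumption.

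The protocol has several routes that end follow-up rather than just treatment. Section 7.2 lists "Lack of efficacy" among the reasons for withdrawal from the study. Section 6.3.3 withdraws unblinded participants. Section 10.14 takes participants with a drug-related seizure out of the study. Suboptimal Response is the most exposed endpoint, because it can be met only after Week 26 and anyone lost earlier cannot meet it. At stake is a flare and failure profile that reads somewhat too favourably when the results are used for Phase 3 planning.

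**Working it through.** **Inputs.**
- LN arms compared: 30 and 30, with 10% anticipated dropout (protocol 9.2). That figure belongs to the sample size for the Week 26 endpoint. Applying it to Week 50 is an assumption.
- Renal flare risk: up to 25% within 1 year (protocol 2.2.3). This is an upper background figure and not a trial assumption, so 10% and 40% were also run.
- Dropout above 10% is assumed throughout.

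**The plan's own figure.** The documents give no size, event count or power for these four endpoints. The LN power statement that carries the 10% dropout does reproduce. With 27 per arm, a difference of ln(0.60/0.40) = 0.4055, SD 0.60 and 1-sided 0.05:
0.4055 / (0.60 × √(2/27)) − 1.645 = 0.838, a power of 79.9% (79.0% with the noncentral t), against a stated figure of about 80%.

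**Crude percentage under loss.** Let F be the true risk to Week 50 and D the dropout to Week 50, with constant independent hazards a = −ln(1−F) and b = −ln(1−D). The expected crude percentage is
a/(a+b) × [1 − (1−F)(1−D)].

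For F = 0.25, a = 0.2877.
- D = 0.10: b = 0.1054; 0.7319 × (1 − 0.675) = 23.8%.
- D = 0.30: b = 0.3567; 0.4465 × (1 − 0.525) = 21.2%.
- D = 0.50: b = 0.6931; 0.2933 × (1 − 0.375) = 18.3%.

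| True risk | 10% dropout | 30% dropout | Gap |
|---|---|---|---|
| 10% | 9.5% | 8.4% | 1.1 points |
| 25% | 23.8% | 21.2% | 2.6 points |
| 40% | 38.1% | 34.2% | 3.9 points |

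The last column is the spurious difference when two arms share the same true risk but lose 10% and 30%. With equal loss in both arms there is none.

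**Kaplan-Meier check.** In 4000 simulated samples of 30 with F = 25%, the mean Kaplan-Meier risk at Week 50 was 25.2%, 25.2% and 24.8% at 10%, 30% and 50% dropout. Dropout was simulated as unrelated to outcome, so this shows correction of uninformative loss only.

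**Suboptimal Response.** With events possible only in Weeks 26 to 50, s = 26/50 and a′ = a/(1−s), the crude percentage is
(1−D)^s × a′/(a′+b) × [1 − exp(−(a′+b)(1−s))].
For F = 25%, D = 10%: 0.9467 × 0.8505 × 0.2870 = 23.1%. At 30% dropout it is 19.2%.

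**If the denominator were different.** Dropping participants lost without an event gives crude/[crude + (1−F)(1−D)]: 0.2379/(0.2379 + 0.675) = 26.1% at 10% dropout and 28.8% at 30%. The bias then runs upward, so the denominator needs to be stated.

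**The case against.** The strongest reply is that the effect is small and the endpoints are descriptive. At the only dropout figure in the documents the shortfall is 1.2 points, about 0.4 of a participant in 30 (0.012 × 30), while the Clopper-Pearson interval for 7 of 30 runs from about 10% to 42%. No test or decision rule uses these tables. All of that stands.

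The documents also never say in words that participants lost to follow-up are event-free. SAP 6.1.8 and 6.1.11 treat a response with no urine collections as missing, so a different denominator is conceivable. The FAS basis and the eCRF-absence rule for Treatment Failure make the event-free reading the natural one, but it remains an inference.

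Three stronger readings are tempting, and the documents do not support them.

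- *That everyone who discontinues counts as event-free.* Protocol 7.1 asks participants who stop study drug to continue visits through Week 50, so their flares are still observed. Only lost follow-up matters. For the same reason the discontinuation rule for complete renal response is not a direct mirror image, since it concerns stopping treatment.
- *That a participant who stops drug and then is treated escapes Treatment Failure.* Such participants "may receive treatment consistent with local standard practice for their disease per Investigator judgment", but the definition in protocol 8.1.9 covers additional therapy for a protocol-defined event at any time in the study, on drug or off. If treated for such an event, they count.
- *That the active or placebo arm will look better.* This needs loss to differ between arms, and the documents give no figure for that.

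Kaplan-Meier also does not repair informative withdrawal, such as withdrawal for lack of efficacy. That is correct, and the fix has to allow for it.

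**Conclusion.** The point holds as a gap in method with a modest effect. Four cumulative events are summarized as crude FAS percentages with no censoring and no stated treatment of incomplete follow-up, so participants lost without a recorded event read as event-free and cumulative risk is understated. For a true 25% risk the understatement is about 1.2 points at 10% dropout and 3.8 points (25.0 − 21.2) at an assumed 30%. It is larger for Suboptimal Response: 1.9 points (25.0 − 23.1) and 5.8 points (25.0 − 19.2). These sizes rest on constant hazards, loss unrelated to outcome and an illustrative 25% risk. The dosing pause makes loss above 10% a realistic possibility, but the documents do not quantify it. A systematic advantage for one arm should not be inferred, because that would need unequal loss. Participants who stop drug and remain in follow-up are not affected.

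**What to change.** - **SAP 4.3.1.8 to 4.3.1.10:** beside the crude FAS percentage, add the Week 50 cumulative incidence by arm with a 95% CI, censored at last study contact. Use Kaplan-Meier, or Aalen-Johansen with death as a competing event. State the denominator and show the number followed to Week 50.
- **Treatment Failure (SAP 4.3.1.10):** add a sensitivity analysis that counts study withdrawal for lack of efficacy as failure, since censoring does not correct informative withdrawal. Do not count stops caused by the dosing pause. In an arm of 30, each participant so reclassified moves the rate by 3.3 points (1/30).
- **Suboptimal Response (SAP 4.3.1.11):** keep the FAS percentage and also show the percentage among participants with a post-Week 26 UPCR assessment, labelled as conditional on retention.

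No new data are needed beyond the date of last contact, and Kaplan-Meier is already planned in SAP 4.3.1.6, 4.4.7 and 4.4.9. The cost is SAP wording, a few table rows and slightly higher reported event rates.

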1.2. Schema

The study design schematic for the LN cohort is provided in Figure 1 and for the IgAN cohort in Figure 2.

Figure 1: Study Design Schematic (LN Cohort)

- ^a The optimal dose level will be identified based on the results of the Week 26 Primary Analysis for each cohort. Once identified, all participants on active treatment in that cohort who have at least 50 weeks of treatment will receive the selected optimal dose for the remainder of the study.
- b Participants will receive additional standard of care therapy in the event of a protocol-defined Renal Flare, or severe Extrarenal SLE Flare. Approved novel treatments for LN can be used per the Investigator's discretion. After Week 26, additional standard of care therapy for participants with Suboptimal Response is allowed at the clinical discretion of the Investigator in conversation with the Medical Monitor. However, if a CNI is used, ALXN2050 will need to be discontinued 3 days prior to CNI administration.
- ^c After completion of the Blinded Extended Treatment Period, participants in the placebo group will only receive allowed concomitant therapy during the Open-label Extension Period and will have the option to receive ALXN2050 180 mg bid or the optimal dose (if already identified) if the participant has a Renal Flare as defined in Section 8.1.6 or Suboptimal Response as defined in Section 8.1.8.

Abbreviations: bid = twice daily; CNI = calcineurin inhibitor; LN = lupus nephritis; SLE = systemic lupus erythematosus

Rlinded Initial Evaluation Blinded Extended Treatment Safety Screening Period Open-Label Extension Period Follow-up Period Period (up to 2 years/104 weeks) (up to 6 weeks) (26 weeks) (24 weeks) 30 days Optimal dose ALXN2050 + ALXN2050 180 mg bid + ALXN2050 180 mg bid + llowed concomitant therapy allowed concomitant therapy (N = 24)IgAN ALXN2050 120 mg bid + ALXN2050 120 mg bid + ALXN2050 + allowed concomitant therapy N = 56 Randomization 3:1:3 ALXN2050 + ALXN2050 180 mg bid + allowed concomitant therapy allowed concomitant therapy Placebo bid 4 (N = 12)allowed concomitant therapy ALXN2050 + ALXN2050 120 mg bid + (N = 24)lowed concomitant therapy allowed concomitant therapy (N = 12)Day 1 Week 26 Week 50 Week 154 Week 158 End of Treatment End of Study Primary Analysis Analysis 164 weeks

Figure 2: Study Design Schematic (IgAN Cohort)

Abbreviations: bid = twice daily; IgAN = immunoglobulin A nephropathy

